## **Study Protocol And Statistical Analysis Plan**

### **Aim**

The aim of this study is to compare evidence-based surgical hand scrubbing methods in order to prevent surgical site infections.

### **Study Setting**

This study was conducted at the Department of Operating Room of the Gülhane Training and Research Hospital in Ankara, Turkey between November 2019 and April 2020.

### **Hypothesis**

#### 1. Method

H0: There is no difference between the effectiveness of different surgical hand scrubbing methods on the bacterial flora in the hand

H1: There is a difference between the effectiveness of different surgical hand scrubbing methods on the bacterial flora in the hand.

#### 2. Time

H0: There is no difference between the effectiveness of different the duration of scrubbing time on the bacterial flora in the hand.

H1: There is a difference between the effectiveness of different the duration of scrubbing time on the bacterial flora in the hand.

### **Method and Participants**

The research is a randomized controlled prospective study. The universe of the research will be surgeon and operating room nurses in Gülhane Training and Research Hospital.

### **Sample Size**

The sample size is at least 180 people for one-way analysis of variance with G \* Power version 3.1.19 software to determine a medium level (0.25) effect size between 4 groups at 0.80 power and 0.05 type I error level calculated (Tsai, 2016). Participants will be divided into 4 groups by randomization method.

## **Randomization**

- ✓ Group I: The participants in the first group performed the surgical hand scrubbing for 1 minute and with using nail brush (n=45).
- ✓ Group II: The participants in the second group performed the surgical hand scrubbing for 1 minute and without using a nail brush (n=45).
- ✓ Group III: The participants in the third group performed the surgical hand scrubbing for 2 minute and with using nail brush (n=45).
- ✓ Group IV: The participants in the fourth group performed the surgical hand scrubbing for 2 minute and without using a nail brush (n=45).

## **Inclusion Criteria:**

- Being a surgeon or operating room nurse
- Having six months and more surgical experience
- Agree to participate in the research

## **Exclusion Criteria:**

- Not wanting to participate in the research
- Being allergic to the skin due to surgical antiseptic use
- Being latex allergy
- Wounds and abrasions on the hand and nail edges
- To have used a systematic antibiotic at the data collection stage and within two weeks

## **Volunteers' Exclusion Criteria (Different from Exclusion Criteria):**

- Participants want to leave the research
- Expected surgery time is less than 1,5 hours.
- A tear / puncture in the glove during the operation.
- During the operation, data collection will be terminated in cases where the sterility of the glove is impaired.

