## **Data Collection**

This research will take place in three stages. At all stages (before surgical hand scrubbing, immediately after and at the end of the surgery), culture will be taken from the active hands of the participants with the Glove Juice Method. At all stages, culture will be taken from the participants via Glove Juice Method.

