## **Statistical Analysis**

The data obtained from this study were evaluated by using the Statistical Package for the Social Sciences (SPSS, Inc., Chicago, IL, USA) 22.0 software program. After the data were transferred to the SPSS database, error controls were performed. Their compliance with a normal distribution was evaluated with Kolmogorov Smirnov test. The data determined were mean  $\pm$  standard deviation ( $X \pm SS$ ), median and minimum-maximum (min-max) for the variables determined by the measurement and number (n) and percent (%) for the variables determined by counting. Since the variables determined by counting did not comply with a normal distribution, the difference between the four groups was evaluated by the Chi square test. The one-way ANOVA test was used to investigate the difference between the four groups regarding the measured values for values complying with normal distribution and the Kruskal-Wallis test was used for the values that did not comply with a normal distribution. The Bonferroni correction was implemented to determine the source of the difference in group comparisons. In the comparison of four measurements within the group, the "Friedman Test" was used for data that did not conform to normal distribution. In order to understand from which measurement the difference arises, "Wilcoxon Test with Bonferroni Correction" was used as Post Hoc Test. The Mann-Whitney U test was used to investigate the difference between two groups of variables. A p value  $<0.05$  was accepted as statistically significant.

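### The end-of-surgery comparison of the four groups is unadjusted; leaving out role and the pre-scrub count may give up precision that would cost almost nothing to recover

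*Combined protocol and SAP*

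**What the plan says.** - **Sample size.** The Sample Size section states: "The sample size is at least 180 people for one-way analysis of variance", chosen "to determine a medium level (0.25) effect size between 4 groups at 0.80 power and 0.05 type I error level". No covariate is mentioned.
- **Allocation.** "Participants will be divided into 4 groups by randomization method". The Randomization section gives 45 per group. Stratification by role or by operation length is not described.
- **Role.** The inclusion criteria require "Being a surgeon or operating room nurse", so role is known at entry.
- **Sampling.** Data Collection: "At all stages (before surgical hand scrubbing, immediately after and at the end of the surgery), culture will be taken". Every participant is therefore due a count before the scrub as well as one at the end of the operation.
- **Operation length.** The second list of exclusion criteria, which also contains events during surgery such as glove damage, includes "Expected surgery time is less than 1,5 hours". It gives a lower limit and no upper one. The documents do not say when the judgement is made or whether a figure is written down.
- **Between-group analysis.** The Statistical Analysis section: "The one-way ANOVA test was used to investigate the difference between the four groups regarding the measured values" when these are normally distributed, with Kruskal-Wallis otherwise. Bonferroni-corrected follow-up comparisons and a Mann-Whitney test for unnamed variables are added. No regression, analysis of covariance or stratified analysis appears.

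**The concern.** Randomisation makes the four groups comparable on average. It does not remove the variation between people that known characteristics explain. In an unadjusted comparison that variation stays in the error term. A person's count before scrubbing, and whether that person is a surgeon or a nurse, are both fixed before the scrub, so a model may use them without risk of adjusting away part of the scrub's effect.

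If they predict the end-of-surgery count, the unadjusted test has wider intervals and lower power than the same 180 people could give. The planned power clears 0.80 by only 0.004, so the design has no margin of its own. What is at stake is efficiency: there is no bias, and the sample size is not in error.

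**Working it through.** **Inputs.** From the Sample Size and Randomization sections: N = 180, k = 4 groups of 45, Cohen's f = 0.25, alpha = 0.05. Not in the documents, so assumed over a range: R², the share of within-group log10 CFU variance that the covariates jointly explain.

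**Step 1: reproduce the plan's figure.** One-way ANOVA power comes from the noncentral F distribution with λ = N·f² and df = k − 1 and N − k.
- 45 per group: λ = 180 × 0.0625 = 11.25, df = 3 and 176, power 0.804.
- 44 per group: λ = 176 × 0.0625 = 11.00, df = 3 and 172, power 0.794.

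The smallest equal-group design that reaches 0.80 is 180, so the stated figure reproduces.

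**Step 2: add two covariates (role and pre-scrub log10 CFU).** Now λ = N·f²/(1 − R²), with df = 3 and 180 − 6 = 174. The standard error is multiplied by √(1 − R²). The unadjusted sample carrying the same information is 180/(1 − R²).

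| Assumed R² | λ | Power | SE multiplier | Equivalent unadjusted N | N for 0.80 power, adjusted |
|---|---|---|---|---|---|
| 0 | 11.25 | 0.804 | 1.000 | 180 | 180 |
| 0.05 | 11.84 | 0.826 | 0.975 | 189 | 172 |
| 0.10 | 12.50 | 0.847 | 0.949 | 200 | 164 |
| 0.20 | 14.06 | 0.890 | 0.894 | 225 | 144 |

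A third covariate (expected operation length) takes one more degree of freedom, leaving 173. At a given R² this moves power by about 0.0001.

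**Step 3: price the case where the covariates are useless.** On degrees of freedom alone, power at R² = 0 goes from 0.8040 to 0.8039. Chance imbalance in the covariates also inflates the variance, by about 1 + q/(N − k − q − 1) for q covariates. With q = 2 this is 1 + 2/173 = 1.0116, which gives power 0.799 at R² = 0. Break-even against the unadjusted 0.804 is at R² of about 0.012. With the same allowance, power at R² = 0.05, 0.10 and 0.20 is 0.821, 0.843 and 0.886.

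**Limits.** These figures are for the 3-df omnibus test on normally distributed values. The separate method and time hypotheses were not computed, and the gains do not carry over to the Kruskal-Wallis branch.

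**The case against.** The strongest reply is that no loss is shown. The documents report no association of role, pre-scrub count or operation length with CFU. If there is none, adjustment gains nothing and costs up to half a point of power. The unadjusted comparison is valid under randomisation, and the planned 180 is correct for it. All of this stands, and it is why the point is worded as a possible loss.

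Four stronger readings are tempting, and the documents support none of them:

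- **That time under the glove varies widely.** Only a 1.5-hour lower limit is given. No distribution of durations appears, and sampling is confined to the first operations of the morning.
- **That expected operation length is known for every participant before scrubbing.** The word expected suggests a prior judgement, but the rule needs only a yes or no, and it sits in a list with intraoperative events. No numeric value is shown to exist.
- **That power is lowered for both hypotheses.** Only the omnibus test was calculated, and the Sample Size section does not tie its 0.80 to the end-of-surgery sample.
- **That the whole model can still be changed.** Study Setting describes the study in the past tense, with dates from November 2019 to April 2020, while other sections use the future tense. If collection is over, an expected length that was not recorded cannot be added.

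Two practical objections also stand. A log-scale model needs a rule for zero counts, which are possible after an antiseptic scrub. It would also replace a rank test that makes fewer assumptions.

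**Conclusion.** The point holds as a minor, conditional one. The plan makes no use of two pre-scrub variables in the end-of-surgery comparison, and this may give up precision. Role is settled at eligibility and the pre-scrub count is planned for everyone, so neither depends on an inference about what was recorded for operation length.

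The gain in omnibus power is about 2, 4 or 9 percentage points at an assumed joint R² of 0.05, 0.10 or 0.20. At R² = 0 there is no gain, and a cost of at most about 0.005. The trade is lopsided in favour of adjustment, but its size rests wholly on an R² that the documents do not give. It also assumes that log10 CFU suits a linear model and that the Sample Size parameters apply to the end-of-surgery count. Nothing here implies a biased comparison or a wrong sample size.

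**What to change.** In the Statistical Analysis section, specify a linear model for end-of-surgery log10 CFU containing the randomised factors (brush, scrub duration and their interaction, which together use the same 3 df as the four groups), pre-scrub log10 CFU, and role. Add three conditions:

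- **Zero counts.** State the rule, for example log10(CFU + 1), and the unit in which the 1 is added.
- **Operation length.** Include expected surgery time only if a pre-scrub value was recorded, or can be recorded, when the 1.5-hour rule is applied. Do not use actual duration, which arises after randomisation.
- **Timing.** If the data have already been seen, label the adjusted analysis post hoc and keep the unadjusted comparison as planned.

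The cost is two or three of 176 error degrees of freedom, a few sentences in the plan, possibly one field on the data form, and reliance on a log-scale linear model in place of the rank test. No further participants or procedures are needed.

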## **The interventions**

### *Standard Protocol in All Groups*

- The application will take place during the first surgeries entered in the morning.

- All groups will be used hand antiseptic (4% Chlorhexidine gluconate) which is used in the operating room.
- It will be examined whether the nails are smaller than 2 mm. If the nails are long, individuals will be asked to cut their nails with the help of disposable nail scissors before surgical hand scrubbing.
- There will be no nail polish on the nails and there will be no jewelry on the hand and the ring.
- 3 ml of antiseptic solution will be used at each washing stage.

### *Scrubbing Stage*

Group I: Surgical hand scrubbing group using a brush (only nails) (Total scrubbing time 1 min)

1. The bottom of the nails is cleaned under running water with a disposable nail brush (30 seconds).
2. Hands and forearms are washed by scrubbing them towards the elbow for 30 seconds with the help of 3ml antiseptic solution.
3. Hands and forearms are thoroughly rinsed under running water.
4. Hands and forearms are washed by scrubbing them towards the elbow for 30 seconds again with the help of 3 ml antiseptic solution.
5. Hands and forearms are rinsed thoroughly under running water.

Group II: Surgical hand scrubbing group (Control group) without brush (Total scrubbing time 2 min)

1. Hands and forearms are washed by scrubbing towards the elbow for 30 seconds with the help of 3 ml antiseptic solution.
2. Hands and forearms are thoroughly rinsed under running water.
3. Hands and forearms are washed by scrubbing them towards the elbow for 30 seconds again with the help of 3 ml antiseptic solution.
4. Hands and forearms are rinsed thoroughly under running water.

Group III: Surgical hand scrubbing group using a brush (only nails) (Total scrubbing time total 2 minutes)

Applications made in Group I are applied in the same way as scrubbing for 2 minute.

Group IV: Surgical hand scrubbing group (Control group) without brush (Total scrubbing time 2 minutes)

Applications made in Group IV are applied in the same way as scrubbing for 2 minute.

## **Data Collection**

This research will take place in three stages. At all stages (before surgical hand scrubbing, immediately after and at the end of the surgery), culture will be taken from the active hands of the participants with the Glove Juice Method. At all stages, culture will be taken from the participants via Glove Juice Method.

### *Glove Juice Method*

It is a method used to determine the number of bacteria on hand. In this method, individuals will be provided to wear gloves on their dominant hand. Powder-free sterile gloves were used for all sampling. Then, 50 ml of 'Tryptic Soy Broth' medium was placed inside the glove and all surfaces of the gloved hand were massaged for 60 seconds by the researcher. A sample was taken from the liquid in the glove using aseptic techniques and analyzed.

### *Applications in Medical Microbiology Laboratory*

Before surgical hand scrubbing, samples taken with glove liquid technique were diluted 1:10 in Müller Hinton Broth broth in the laboratory (500  $\mu$ l sample, 4.5 ml. Müller Hinton Broth). And 300  $\mu$ l of it was placed on 5% sheep blood agar plates with sterile micropipettes. 1 ml each of the other samples (after surgical hand scrubbing and at the end of the surgery) was spread diluted into three 5 % sheep blood agar plates with sterile micropipettes. All samples were incubated at 35° C for 48 hours under atmospheric conditions. Total bacterial load was determined by counting the total colony forming units (CFU) on the plates.

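### Bacterial load is defined as the raw plate count, although one colony stands for about 33 times more bacteria before scrubbing than after it on the plain reading

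*Combined protocol and SAP*

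**What the plan says.** The combined protocol and SAP samples each participant at three stages (Data Collection): before scrubbing, immediately after it, and at the end of surgery. Of the glove juice method it says "It is a method used to determine the number of bacteria on hand". The sampling fluid is 50 ml of broth; this "medium was placed inside the glove and all surfaces of the gloved hand were massaged for 60 seconds".

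The section Applications in Medical Microbiology Laboratory then handles the stages differently:

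- Baseline: "Before surgical hand scrubbing, samples taken with glove liquid technique were diluted 1:10 in Müller Hinton Broth broth in the laboratory" (500 µl of sample plus 4.5 ml of broth), and 300 µl "of it was placed on 5% sheep blood agar plates with sterile micropipettes".
- Post-scrub and end of surgery: the amount plated is "1 ml each of the other samples (after surgical hand scrubbing and at the end of the surgery"), and the text says that this amount "was spread diluted into three 5 % sheep blood agar plates". No dilution factor is given.

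The outcome is then stated once, for all stages: "Total bacterial load was determined by counting the total colony forming units (CFU) on the plates". Neither this section nor Statistical Analysis multiplies by a dilution factor, divides by a plated volume, or scales to the 50 ml in the glove. Statistical Analysis specifies a Friedman test for non-normal data ("In the comparison of four measurements within the group"), followed by Bonferroni-corrected Wilcoxon tests.

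**The concern.** A colony count measures bacteria on the hand only after correction for the share of the glove fluid that reached the plate. That share is much smaller at baseline than later, so a raw count understates baseline relative to the later stages.

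Rank tests do not protect against this. Friedman and Wilcoxon tests compare stages within a person, and multiplying one stage by a constant changes those ranks and signs. The descriptive means and medians by stage carry the same gap.

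Two results are at stake: whether scrubbing lowered the count, and whether the count at the end of surgery is still below baseline. Either can be wrong in size and, depending on the true reduction and the laboratory details, in direction.

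**Working it through.** **Inputs.** From Glove Juice Method: 50 ml of fluid. From the laboratory section: 0.5 ml sample plus 4.5 ml broth, 0.3 ml plated at baseline, 1 ml over three plates later.

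**Stated dilution.** 0.5 / (0.5 + 4.5) = 0.10, which agrees with the plan's 1:10.

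**Scale at each stage.** The plain reading takes later samples as undiluted, 1 ml in total, with the three plates summed.

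- Baseline: 0.3 ml × 0.10 = 0.03 ml of glove fluid; 50 / 0.03 = 1,667 CFU per hand per colony.
- Later: 1 ml of glove fluid; 50 / 1 = 50 CFU per hand per colony.
- Ratio R = 1,667 / 50 = 33.3.

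**Other readings.** The text leaves four details open:

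- whether the baseline 0.3 ml went on one plate, was split over three, or went on each of three;
- whether the later 1 ml was split over three plates or put on each;
- whether later samples were diluted (none, or 1:10 as an assumption);
- whether plates were summed or averaged (taken as the same at all stages).

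These give 3 × 2 × 2 × 2 = 24 combinations but only six values of R. The apparent post/pre ratio is R × (1 − true reduction), so the true reduction that looks like no change is 1 − 1/R.

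| Later samples | R | True reduction seen as no change | Apparent post/pre ratio at a true 90% reduction |
|---|---|---|---|
| Undiluted | 11.1 | 91% | 1.1 |
| Undiluted | 33.3 | 97% | 3.3 |
| Undiluted | 100 | 99% | 10 |
| 1:10 (assumed) | 1.11 | 10% | 0.11 |
| 1:10 (assumed) | 3.33 | 70% | 0.33 |
| 1:10 (assumed) | 10 | 90% | 1.0 |

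The floor of 1.11 needs, besides the assumed dilution, either averaging over plates (0.0333 / 0.03) or three baseline plates of 0.3 ml each, summed (0.1 / 0.09).

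**Example at R = 33.3**, assuming a baseline of 100,000 CFU per hand. Expected colonies before scrubbing: 100,000 × 0.03 / 50 = 60. After a true 90% reduction: 10,000 × 1 / 50 = 200. The count rises although the load fell tenfold. A true 99% reduction gives 0.01 × 33.3 = 0.33, an apparent fall of 67%.

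**Effect on the Wilcoxon test.** Simulation with 45 people, threshold 0.05 / 3 = 0.0167, raw plate counts and a true 90% reduction. Assumed inputs: baseline median 100,000 CFU per hand, SD 0.5 log10 between people and 0.3 log10 in the change, Poisson counts, 400 runs.

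- R = 33.3: significant rise in 100% of runs.
- R = 11.1: not significant in 85%, significant rise in 15%.
- R = 1.11: significant fall in 100%.

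A second simulation (SD of change 0.4 log10, 500 runs) took a true 33-fold reduction at R = 33.3. Raw counts reached significance in 5% of runs; counts converted to a common scale did so in 100%.

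**The case against.** The strongest reply is that the sentence on colony counting describes how bacteria were enumerated and does not forbid back-calculation. The plan names bacteria on the hand as its target and records nearly all the volumes needed to convert, so the laboratory may well have done so. That is possible, but nothing in the document says it, and an analyst who follows the only stated rule uses raw counts.

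Second, the later samples are described as diluted, so 33-fold is not established. This stands in part. The 1 ml is of the sample itself and no factor is given, which makes 33 the natural reading; an unstated 1:10 dilution would bring the ratio down to between 1.1 and 10, and a larger one would lower it further. The true ratio cannot be fixed from the document.

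Third, both hypotheses compare scrubbing methods and durations, which are between-group questions, and no change score is specified. This is correct and limits the damage. The Friedman variable is also not named; that it is the colony count by stage is an inference, though a natural one.

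Fourth, reversal of direction depends on the true reduction, for which the document gives no expected value. At a true 90% reduction, only the undiluted readings show a rise; at 99%, none does.

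Finally, conversion does not equalise detection limits: on the plain reading, one colony remains 1,667 CFU per hand at baseline and 50 later. That is a fair caveat on zero counts, not a reason to leave the scales unequal.

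**Conclusion.** The concern holds and should be fixed. The stated outcome rule puts baseline on a different scale from the later stages, by 33-fold on the plain reading. The size depends on laboratory details the plan does not give, and at the lowest reading (1.1) the distortion is negligible. The simulated error rates rest on assumed baseline counts and variances; the scale ratio does not.

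Affected if the rule is followed as written: the Friedman test, the two Wilcoxon pairs involving baseline, and descriptive comparisons with baseline. Not affected: same-stage comparisons between groups, post-scrub versus end of surgery (plated alike), and the sample size. Confidence is high that the conversion is missing; whether the reported results were distorted depends on what the laboratory did.

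**What to change.** Define the outcome at every stage as

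CFU per hand = colonies × dilution factor × 50 ml / volume plated,

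and use it for every comparison and summary that involves baseline. The volume must match the count: total volume if plates are summed, volume per plate if averaged. For each stage, state the dilution, the number of plates, the volume per plate, and whether plates are summed or averaged. If conversion was already done, say so and give the formula. The planned rank tests can stay; analysis on the log10 scale is optional. A zero count should be read against its own stage's detection limit.

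A separate, minor correction: Statistical Analysis refers to four within-group measurements, but Data Collection has three. With three, the Bonferroni threshold for the pairwise Wilcoxon tests is 0.05 / 3 = 0.0167.

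The cost is a few sentences and a recalculation from existing plate counts and laboratory records, with no new samples or participants.
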